4.4.2.5. Other Analysis: Efficacy PP Population

To mitigate for the impact of the COVID-19 pandemic, mNIS+7 will also be analyzed using the Efficacy PP population; full details are provided in [Section 4.9.2](#).

4.4.2.6. Overview of Primary Endpoint Analyses

The planned analyses of the primary endpoint mNIS+7 are summarized in [Table 4](#).

Table 4: Analysis of Primary Endpoint mNIS+7

Statistical Method
Month 9: ANCOVA/MI
Month 18: MMRM
Sensitivity analysis: Including data post local standard treatment for hATTR amyloidosis or post serious COVID-19 AE (Month 9: ANCOVA ; Month 18: MMRM)
Sensitivity analysis: Propensity score (Month 9: propensity-adjusted ANCOVA ; Month 18: propensity-adjusted MMRM)
Sensitivity analysis: Pattern-mixture model with modified ANCOVA/MI at Months 9 and 18
Other analysis: Binary endpoint analysis using stratified CMH
Other analysis: Efficacy PP Population (Month 9: ANCOVA ; Month 18: MMRM)

4.4.3. Secondary Efficacy Evaluations

4.4.3.1. Key secondary endpoint: Norfolk QoL-DN Total Score

Change from baseline in Norfolk QoL-DN total score (primary analysis incorporating COVID-19 pandemic impact questions, described in Section 9.1.2) will be analyzed using an [ANCOVA/MI](#) model at Month 9, and using an [MMRM](#) at Month 18. Sensitivity, binary, and Efficacy PP Population analyses for Norfolk QoL-DN total score will also be conducted as described for mNIS+7 in Section 4.4.2.

An additional sensitivity analysis of change from baseline in Norfolk QoL-DN total score (without incorporating COVID-19 impact questions, described in Section 9.1.2) will be analyzed using an [ANCOVA/MI](#) model at Month 9, and using an [MMRM](#) at Month 18.

4.4.3.2. 10-meter Walk Test Speed, mBMI, and R-ODS

For 10-meter walk test speed (Section 9.1.4), mBMI (Section 9.1.5), and R-ODS (Section 9.1.6), change from baseline will be analyzed using an [ANCOVA/MI](#) model at Month 9 (with mBMI and R-ODS analyzed at Month 9 as exploratory endpoints), and using an [MMRM](#) at Month 18. Binary analyses for 10-meter walk test speed will also be conducted as described for mNIS+7 in Section 4.4.2.4.

4.4.3.3. Time-averaged Trough TTR Percent Reduction

Time-averaged trough TTR percent reduction through Month 18 is defined as the average trough (ie, predose) TTR percent reduction from Month 6 to 18, which is the steady state period for both vutrisiran and patisiran. Only trough TTR assessments meeting requirements described in the TTR PP population definition (Section 2; Table 3) will be included. The Hodges-Lehmann method [[Hodges and Lehmann 1962](#)], stratified by previous TTR stabilizer use (yes vs no), where values within each stratum are first aligned by the within-stratum 1-sample Hodges-Lehmann median, will be used to estimate the 95% CI for the median difference between the vutrisiran and patisiran groups in this study. Non-inferiority of vutrisiran (versus patisiran) will

be declared if the lower limit of the 95% CI for the median treatment difference in TTR percent reduction (vutrisiran – patisiran) in this study is greater than –10%.

Sensitivity analyses using the same analysis method will be conducted to compare the TTR percent reduction through Month 18 between the vutrisiran group from this study and the pooled patisiran group from this study and the APOLLO study.

4.4.3.4. Overview of Secondary Endpoint Analyses

The planned analyses of the secondary endpoints are summarized in [Table 5](#).

Table 5: Analysis of Secondary Endpoints

Endpoint	Statistical Method	Analysis Population	Special Notes
Norfolk QoL-DN total score	Month 9: ANCOVA/MI Month 18: MMRM	mITT	Derivation described in Section 9.1.2 Sensitivity and binary analyses described in Section 4.4.2
10-meter walk test speed	Month 9: ANCOVA/MI Month 18: MMRM	mITT	Derivation described in Section 9.1.4 Binary analyses described in Section 4.4.2.3
mBMI	Month 9 (exploratory endpoint): ANCOVA/MI Month 18: MMRM	mITT	In APOLLO study, mBMI was not assessed at Months 9 or 18. The average values of Day 189 and Day 357 will be derived as Month 9. Day 546 will be used as Month 18.
R-ODS	Month 9 (exploratory endpoint): ANCOVA/MI Month 18: MMRM	mITT	Derivation described in Section 9.1.6
TTR percent reduction through Month 18	Stratified Hodges-Lehmann	TTR PP	Sensitivity analysis comparing against patisiran (HELIOS-A + APOLLO)

4.4.4. Exploratory Efficacy Evaluations

The exploratory continuous endpoints, including change from baseline in NIS ([Section 9.1.1.2](#)), EQ-5D-5L index ([Section 9.1.3](#)), and EQ VAS, will be analyzed using an [ANCOVA/MI](#) model at Month 9, and using an [MMRM](#) at Month 18. For EQ-5D-5L, categorical descriptives for ordinal response within each EQ-5D domain will be presented at each visit.

The exploratory categorical endpoints, PND score, FAP stage, NYHA class, and KPS, will be descriptively summarized by presenting categorical descriptives for each visit. Categorical descriptives for patients with improving, no change, and worsening in PND/FAP at each postbaseline visit will also be summarized.

Cardiac structure and function will be assessed for all patients through echocardiograms. Cardiac stress and injury will be measured using serum levels of the cardiac biomarkers NT-proBNP,

troponin I, and troponin T. Quantification of these biomarkers will be performed at a central laboratory. Descriptive statistics will be provided for actual values, changes, and percentage changes from baseline in echocardiogram parameters and serum levels of troponin I, troponin T, and NT-proBNP by treatment group at each visit.

For the mITT Population and Cardiac Subpopulation, select echocardiographic parameters will be analyzed using an [MMRM](#) at Month 18 with covariate (baseline value), factors (treatment group; visit [Month 9; Month 18]), and an interaction term (treatment group by visit), including:

- Mean left ventricular (LV) wall thickness
- LV mass
- Global longitudinal strain
- LV end-diastolic volume
- Cardiac output

Cardiac biomarker NT-proBNP will be analyzed for the mITT population and Cardiac Subpopulation using an [ANCOVA/MI](#) model with covariate (baseline) and factor (treatment group) at Month 9. Additionally, NT-proBNP will be analyzed at Month 18 for the mITT population and Cardiac Subpopulation using an [MMRM](#) with covariate (baseline value), factors (treatment group; visit [Month 9; Month 18]), and an interaction term (treatment group by visit). A logarithmic transformation will be applied to both baseline and change from baseline values to normalize the data before fitting the MMRM. The adjusted geometric mean fold-change and the ratio of the fold-change (vutrisiran/placebo) from baseline will be presented.

For the mITT Population and Cardiac Subpopulation, change from baseline in heart-to-contralateral lung ratio and normalized LV total uptake of injected dose as assessed by technetium scintigraphy will be summarized at Month 18. Perugini grade as assessed by technetium scintigraphy will be descriptively summarized by presenting categorical descriptives for each visit. Additional Technetium parameters may be descriptively summarized.

All echocardiogram, cardiac, and technetium scintigraphy data will be presented in data listings.

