3.4. Randomization Stratification Factors

Stratification factors for randomization into the 18-Month Treatment Period include TTR genotype (V30M vs. non-V30M) and baseline NIS score (< 50 vs. ≥ 50).

Stratification factors are recorded in both the Interactive Response System (IRS) and the clinical database. In statistical analyses that use randomization stratification factors as covariates, the stratum assignment will reflect the values as recorded in the clinical database. In the presence of stratification errors, the stratification used in analysis may not match that in the IRS.

In addition to the initial randomization, [REDACTED]

[REDACTED] For patients initially randomized to vutrisiran, stratification factors for this 2nd randomization include TTR genotype (V30M vs. non-V30M) and the most recent FAP stage (0/1 vs 2/3) before the 2nd randomization. For patients initially randomized to patisiran, there is no stratification for this 2nd randomization.

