4.4. Efficacy Evaluation

This Phase 3 study will use the APOLLO study as an external control. Patient-level data from this study will be compared with patient-level data from APOLLO for efficacy analyses.

Except for TTR endpoints, analysis models will include only the 2 treatment groups compared, vutrisiran and placebo (APOLLO), and only simple descriptives will be presented for patisiran (HELIOS-A). For TTR endpoints, vutrisiran and patisiran (HELIOS-A) will be compared unless otherwise specified.

For efficacy endpoints, 2-sided 95% confidence intervals and 2-sided nominal P values will be presented if applicable unless otherwise specified. Formal multiplicity-controlled hypothesis testing will be conducted as described in Section 1.3.1; all other P values presented will be considered descriptive.

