4.4.1.1. ANCOVA/MI

ANCOVA incorporating MI will be the default analysis for most continuous efficacy endpoints at Month 9.

MI is a broadly applicable technique for handling missing data. Missing data are imputed multiple times using a regression method. Each imputed data set is analyzed using the same analysis model, and the point estimates and standard errors are combined to provide inferences that reflect the uncertainty about the missing values. MI assumes the data are missing at random (MAR).

For a given endpoint, missing endpoint values will be multiply imputed separately for each treatment group using a regression procedure, with baseline information including baseline score and KPS as covariates and genotype, age at hATTR symptom onset, prior tetramer stabilizer use, region, FAP stage (I vs. II/III), Cardiac subpopulation, sex, and baseline NIS (<50 vs. ≥50) as factors. For NIS-related endpoints, the categorical baseline NIS score will not be included in the regression procedure.

One hundred imputed datasets (per treatment group) will be generated from the MI regression procedure using SAS PROC MI. Each of the imputed datasets will then be analyzed using an ANCOVA model, including a covariate (baseline value) and factors (treatment group; genotype; age of disease onset, baseline NIS score [<50 vs ≥ 50]), unless otherwise specified. For NIS-related endpoints, the categorical baseline NIS score will not be included in the model.

The resulting estimates (LS mean differences and standard errors) from the 100 imputed datasets will be combined using SAS PROC MIANALYZE to produce inferential results (difference in LS means, 95% CI for the difference, and the P value from the test that the difference is zero). [Rubin 1996] Combined LS mean estimates will be calculated as the average of the 100 complete-data estimates. A total variance estimate will be calculated as a weighted sum of within-imputation variance, which is the average of the complete-data variance estimates, and a between-imputation variance term. Complete details may be found in the SAS documentation for the MIANALYZE procedure (see Combining Inferences from Imputed Data Sets under Details: <http://support.sas.com/documentation/onlinedoc/stat/131/mianalyze.pdf>).

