4.4.1.2. MMRM

MMRM will be the default analysis for most continuous efficacy endpoints at Month 18. MMRM makes use of fully and partially observed data sequences from individual patients by estimating the covariance between data from different time points. The MMRM will be implemented using an unstructured approach to modeling both the treatment-by-time means and the (co)variances, leading to what is essentially a multivariate normal model wherein treatment group means at the primary time point are adjusted to reflect both the actually observed data and the projected outcomes from the patients with missing data. MMRM also assumes data are missing at random (MAR).

For most endpoints, the MMRM will include a covariate (baseline value), factors (treatment group; visit [Month 9; Month 18]; genotype; age of disease onset; baseline NIS score [<50 vs ≥ 50]), and an interaction term (treatment group by visit), unless otherwise specified. For NIS-related endpoints, the categorical baseline NIS score will not be included in the model.

LS mean and mean difference estimates, SEs, 95% CIs, and p-values at Month 9 and Month 18 will be presented.

An unstructured covariance structure will be used to model the within-patient errors. If the model fails to converge, the following covariance structures will be specified in sequence and the first to converge will be used:

1. Toeplitz
2. First order autoregressive
3. Compound symmetry

The Satterthwaite approximation will be used to estimate the degrees of freedom.

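### The NT-proBNP and echocardiography models omit genotype, onset age and baseline NIS from a non-randomised comparison, so differences between the trials in these factors can enter the exploratory cardiac estimates

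*SAP*

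**What the plan says.** All references are to SAP Amendment 3 unless stated.

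- **Cardiac models (Section 4.4.4).** NT-proBNP is analysed in the mITT population and the Cardiac Subpopulation by an ANCOVA/MI "model with covariate (baseline) and factor (treatment group) at Month 9". Five echocardiographic parameters are analysed by MMRM in the same two populations "at Month 18 with covariate (baseline value), factors (treatment group; visit [Month 9; Month 18]), and an interaction term (treatment group by visit), including" LV wall thickness, LV mass, strain, end-diastolic volume and cardiac output. The NT-proBNP MMRM at Month 18 has the same terms. For NT-proBNP, "the ratio of the fold-change (vutrisiran/placebo) from baseline will be presented".
- **Comparator (Section 4.4).** Outside the TTR endpoints, "analysis models will include only the 2 treatment groups compared, vutrisiran and placebo (APOLLO"). The contrast is therefore between two trials.
- **Default models.** The ANCOVA/MI in Section 4.4.1.1 has "factors (treatment group; genotype; age of disease onset, baseline NIS score" in two categories, plus the baseline value. The MMRM in Section 4.4.1.2 likewise has "genotype; age of disease onset; baseline NIS score". Both defaults apply unless another model is specified, and Section 4.4.4 specifies another.
- **Further adjustment.** The propensity-score analysis (Section 4.4.2.2) is for mNIS+7 and extends to Norfolk QoL-DN through Section 4.4.3.1. The subgroup analyses (Section 4.4.5) cover the same two endpoints.

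**The concern.** Randomisation did not form the vutrisiran-versus-placebo contrast, so the analysis has to deal with differences in patient mix between the trials. For the continuous primary and secondary endpoints compared with placebo, the plan does this with the baseline value plus three prognostic factors. For the cardiac endpoints it uses the baseline value alone. The visit and treatment-by-visit terms in the MMRMs describe time and do not adjust for who was enrolled.

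The baseline value removes confounding only to the extent that it captures how a patient will change. If patients of different genotype or onset age progress differently from the same starting NT-proBNP or wall thickness, and the trials enrolled them in different proportions, part of that difference is reported as a treatment effect. What is at stake is the reading of the exploratory cardiac estimates and their confidence intervals.

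Small numbers could justify a shorter model in the Cardiac Subpopulation, although the SAP does not say so. They do not explain one in mITT, where about 120 vutrisiran patients are planned.

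**Working it through.** **The plan's own figure.** There is none for the cardiac endpoints. The stated power above 90% (Section 1.4) concerns mNIS+7 and Norfolk QoL-DN. It is reproduced with 120 vutrisiran patients for any placebo group of at least 16 (mNIS+7) or 19 (Norfolk), but it does not bear on this point.

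**Terms side by side**

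| Model | Baseline value | Genotype | Onset age | Baseline NIS |
|---|---|---|---|---|
| Default ANCOVA/MI and MMRM (4.4.1.1, 4.4.1.2) | yes | yes | yes | yes |
| Subgroup models for mNIS+7 and Norfolk (4.4.5) | yes | yes, except in genotype subgroups | no | no |
| NT-proBNP and echocardiography, mITT and Cardiac Subpopulation (4.4.4) | yes | no | no | no |

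The rule that leaves NIS category out applies to NIS-related endpoints, and the cardiac endpoints are not NIS-related. At Month 9 the imputation regression does contain these factors by default, but it fills in missing values within each group and does not adjust the treatment contrast.

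**Inputs for an illustration.** From the plan: 160 patients randomised 3:1, so 160 × 3/4 = 120 on vutrisiran. Assumed, because the plan does not give them: placebo n of 60 to 90, residual SD of 0.5 on the log scale, prevalence difference D between the trials, and effect γ of a binary factor on log fold-change.

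**Closed form.** Bias in the log ratio = D × γ.

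- D = 0.10, γ = 0.2 (1.22-fold): 0.02, so a true ratio of 1.00 is estimated as 1.020.
- D = 0.20, γ = 0.3 (1.35-fold): 0.06, so it is estimated as 1.062.
- If the imbalance has the opposite sign, the bias reverses.

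SE = 0.5 × √(1/120 + 1/n), which is 0.079 for n = 60 and 0.070 for n = 90. The probability of a nominal two-sided P below 0.05 when there is no effect is then 0.057 and 0.059 for the first case, and 0.118 and 0.138 for the second.

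**Simulation.** 4,000 replicates per setting; true ratio 1.00; 120 versus 60 or 80 patients; factor less common on vutrisiran; baseline value correlated with the factor. Ranges are over the two placebo sizes.

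| D | Factor effect | Ratio, baseline-only model | P < 0.05, baseline-only model |
|---|---|---|---|
| 0.1 | 1.2-fold | 0.982–0.984 | 0.056–0.059 |
| 0.1 | 1.5-fold | 0.962–0.963 | 0.073–0.080 |
| 0.2 | 1.2-fold | 0.965–0.967 | 0.068–0.074 |
| 0.2 | 1.5-fold | 0.928 | 0.136–0.163 |
| 0.3 | 1.2-fold | 0.949–0.951 | 0.103–0.105 |
| 0.3 | 1.5-fold | 0.892–0.894 | 0.264–0.313 |

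With the factor in the model, the mean ratio was 0.999 to 1.003 and the rejection rate 0.046 to 0.055 in every setting. The baseline value absorbed little of the bias: at D = 0.3 and 1.5-fold the closed form gives 0.886, against 0.892–0.894 simulated.

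**Precision.** If the omitted factors have a multiple correlation of 0.3 (0.5) with the change, adjusting for them cuts residual variance by 0.3² = 9% (0.5² = 25%).

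**The case against.** The strongest reply is that the reduced model is an explicit choice for exploratory endpoints and that other safeguards exist. Much of this stands.

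- **The consequence is limited.** The endpoints are in neither testing hierarchy (Sections 1.3.1 and 1.3.2), and Section 4.4 treats P values outside the formal procedure as descriptive. The rejection rates above show how far an estimate can drift relative to its SE; they do not describe an error rate that the plan claims to control.
- **Covariates are not the only protection, as a reader might infer.** The models keep the baseline cardiac value, and Section 1.4 caps patients with NT-proBNP above 3000 ng/L at 15% so that cardiac severity resembles APOLLO. Both address cardiac severity at entry. Neither addresses different progression from the same starting value.
- **These are not the least adjusted comparisons in the plan, though a reader might think so.** The genotype-subgroup models in Section 4.4.5 are equally reduced, and the binary analysis in Section 4.4.2.4 stratifies by genotype but has no baseline value.
- **Stratification does not settle the matter.** Section 3.4 says "Stratification factors for randomization into the 18-Month Treatment Period include TTR genotype (V30M vs. non-V30M) and baseline NIS score" category. That balances vutrisiran against patisiran. It shows that the data are available, but it does not show that these factors predict cardiac change or differ from APOLLO.

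What the reply does not supply is a reason for the shorter model in mITT. The Amendment 3 log says only that the cardiac model details were updated to clarify and support the cardiac evaluation. The superseded Amendment 2 text used the default models for mITT. That change is not itself an error, but it suggests that the fuller model was considered workable.

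**Conclusion.** The point holds as a conditional one. Section 4.4.4 removes three available factors from a non-randomised contrast in the full mITT population without giving a reason, and no other planned analysis adjusts the cardiac endpoints for them. Between-trial differences in genotype, onset age or baseline NIS can enter the estimated cardiac effect if those factors also predict change given baseline.

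A reader might infer that the cardiac results are biased. The document does not support that: it gives neither the imbalance nor the prognostic strength. The 2% and 6% shifts, and the wider simulated range, rest on assumed prevalence differences, factor effects, SD and placebo size, and the direction is unknown. Severity is minor to moderate. The primary and secondary conclusions and the familywise error rate are unaffected.

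**What to change.** In Section 4.4.4:

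1. For the mITT population, use the default covariate set (baseline value, genotype, age at disease onset, baseline NIS below 50 versus 50 or above) in the NT-proBNP ANCOVA/MI at Month 9 and in the NT-proBNP and echocardiography MMRMs at Month 18.
2. Keep the baseline-only model as a sensitivity analysis, so that readers can see how much the adjustment changes the estimate.
3. In the Cardiac Subpopulation, add genotype if numbers allow. The Section 4.4.5 models for mNIS+7 and Norfolk already keep genotype within that subgroup. If numbers do not allow it, state this as the reason.

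The cost is a change of SAP wording and about three degrees of freedom in mITT, one for each two-level factor. The default models already use these covariates for other endpoints, so no new data are needed.

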4.4.4. Exploratory Efficacy Evaluations

The exploratory continuous endpoints, including change from baseline in NIS (Section 7.1.1.2), EQ-5D-5L index (Section 7.1.3), and EQ VAS, will be analyzed using an ANCOVA/MI model at Month 9, and using an MMRM at Month 18. For EQ-5D-5L, categorical descriptives for ordinal response within each EQ-5D domain will be presented at each visit.

The exploratory categorical endpoints, PND score, FAP stage, NYHA class, and KPS, will be descriptively summarized by presenting categorical descriptives for each visit. Categorical descriptives for patients with improving, no change, and worsening in PND/FAP at each postbaseline visit will also be summarized.

Cardiac structure and function will be assessed for all patients through echocardiograms. Cardiac stress and injury will be measured using serum levels of the cardiac biomarkers NT-proBNP, troponin I, and troponin T. Quantification of these biomarkers will be performed at a central laboratory. Descriptive statistics will be provided for actual values, changes, and percentage changes from baseline in echocardiogram parameters and serum levels of troponin I, troponin T, and NT-proBNP by treatment group at each visit.

For the mITT Population, select echocardiographic parameters will be analyzed using an MMRM at Month 18, including:

- Mean left ventricular (LV) wall thickness
- LV mass
- Global longitudinal strain
- LV end-diastolic volume
- Cardiac output

Additionally, these select echocardiographic parameters will be analyzed at Month 18 for the Cardiac Subpopulation using an MMRM with covariate (baseline value), factors (treatment group; visit [Month 9; Month 18]), and an interaction term (treatment group by visit).

Cardiac biomarker NT-proBNP will be analyzed for the mITT population using an ANCOVA/MI model at Month 9, and using an MMRM at Month 18. Additionally, NT-proBNP will be analyzed at Month 18 for the Cardiac Subpopulation using an MMRM with covariate (baseline value), factors (treatment group; visit [Month 9; Month 18]), and an interaction term (treatment group by visit). A logarithmic transformation will be applied to both baseline and change from baselines values to normalize the data before fitting the MMRM. The adjusted geometric mean fold-change and the ratio of the fold-change (vutrisiran/placebo) from baseline will be presented.

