4.4.2.2. Sensitivity Analysis: Propensity Score

To allow some control of more factors and covariates without saturating the model, a propensity score approach will be used to reduce the predictors to a single propensity score. The propensity score is defined as the probability of being treated with vutrisiran as obtained from a logistic

regression model of treatment group [vutrisiran; placebo (APOLLO)]. The logistic regression model will include the following baseline variables:

- Continuous variables
 - NT-proBNP (log-transformed)
 - mNIS+7
 - Norfolk QoL-DN total score
- Categorical variables
 - Previous tetramer stabilizer use (tafamidis/diflunisal) [Yes; No]
 - Karnofsky Performance Status (KPS) [60; 70-80; 90-100]
 - Cardiac Subpopulation [Yes; No]
 - PND score [I; II; IIIA; IIIB/IV]
 - Age at hATTR Symptom onset [< 50 ; ≥ 50]
 - Neuropathy Impairment Score (NIS) [< 50 ; ≥ 50]
 - Genotype [V30M; non-V30M]
 - FAP stage [I; II/III]

The primary endpoint will be analyzed in this sensitivity analysis using the [ANCOVA](#) method at Month 9 and [MMRM](#) method at Month 18, including the propensity score covariate in addition to the default model factors and covariates.

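### The NT-proBNP analysis takes the log of the change from baseline instead of the change in log values, and leaves the scale of the Month 9 ANCOVA/MI unstated

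*SAP*

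**What the plan says.** Section 4.4.4 of the current SAP (Amendment 3) plans two models for NT-proBNP, each in the mITT population and in the Cardiac Subpopulation.

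- Month 9: an ANCOVA/MI "model with covariate (baseline) and factor (treatment group) at Month 9".
- Month 18: an MMRM, introduced with "Additionally, NT-proBNP will be analyzed at Month 18 for the mITT population and Cardiac Subpopulation using an". Its terms are baseline, treatment, visit (Months 9 and 18) and treatment by visit.

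The transformation rule follows: "A logarithmic transformation will be applied to both baseline and change from baseline values to normalize the data before fitting the MMRM". The paragraph ends with the output: "The adjusted geometric mean fold-change and the ratio of the fold-change (vutrisiran/placebo) from baseline will be presented".

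Two other places bear on the scale. The general method in Section 4.4.1.1 says "For a given endpoint, missing endpoint values will be multiply imputed separately for each treatment group using a regression procedure" and contains no transformation rule. The propensity model in Section 4.4.2.2 lists baseline "NT-proBNP (log-transformed)" among its continuous variables.

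**The concern.** The rule and the promised output do not describe the same analysis. A change from baseline is a difference, and a difference can be zero or negative; a fall in NT-proBNP is the favourable direction. The logarithm is then undefined for exactly the patients whose marker does not rise. A fold-change, by contrast, is a ratio and comes from a difference of logs.

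The second part concerns Month 9. The log is attached only to the MMRM, while the same paragraph also plans an ANCOVA with multiple imputation. Nothing says whether imputation and modelling there are done on ng/L or on a log scale. At stake are the definition of the response variable in one model and the scale of the other, in two populations. If the plan does not settle them, they will be settled in programming.

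**Working it through.** The plan gives no NT-proBNP distribution or expected effect, so there is no planned figure to reproduce. The check is algebra, with illustrative patient values chosen only to show it.

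**Notation.** B is baseline, P is the postbaseline value, both positive.

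**1. What the rule literally gives.** Response = log(P − B).

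| B to P (ng/L) | P − B | log(P − B) | log P − log B | P/B |
|---|---|---|---|---|
| 1000 to 800 | −200 | undefined | −0.223 | 0.80 |
| 1000 to 1000 | 0 | undefined | 0 | 1.00 |
| 1000 to 1200 | 200 | 5.298 | 0.182 | 1.20 |
| 100 to 300 | 200 | 5.298 | 1.099 | 3.00 |
| 3000 to 3200 | 200 | 5.298 | 0.065 | 1.07 |

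The first two rows show where the stated response does not exist. The last three share one value of log(P − B), yet their fold-changes run from 1.07 to 3.00. The stated response therefore does not carry the fold-change, even among patients whose level rises.

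**2. What the promised output needs.** The geometric mean fold-change in an arm is exp{mean of log(P/B)}, and log(P/B) = log P − log B. If the adjusted arm means of that response are m(vutrisiran) and m(placebo), then exp{m(vutrisiran) − m(placebo)} is the ratio of fold-changes. This response is defined for every row of the table: −0.223 back-transforms to 0.80, 0 to 1.00 and 0.182 to 1.20.

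**3. The Month 9 scale.** Setting the places side by side:

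- Section 4.4.4, Month 9 model: gives the covariate and the factor, no scale.
- Section 4.4.4, transformation sentence: names the MMRM only.
- Section 4.4.4, output sentence: not restricted to either model.
- Section 4.4.1.1: regression imputation within arm, then ANCOVA, with no transformation.
- Section 4.4.2.2: baseline NT-proBNP on the log scale.

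The first, second and fourth, read literally, give an untransformed analysis at Month 9, which would yield a difference in ng/L and no fold-change. The third and fifth point towards a log scale. The text does not decide between them. The scale of the imputation also needs stating in its own right: a linear regression on ng/L can draw values at or below zero, which could not then be logged.

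**4. Which version this is.** The rule is in the current text. Section 4.4.4 of Amendment 2 read: "A logarithmic transformation will be applied to both baseline and change from baselines values to normalize the data before fitting the MMRM". Amendment 3 revised the NT-proBNP models and corrected a plural in this sentence, but kept the rule.

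**The case against.** The best defence is that the sentence on output fixes the meaning. A geometric mean fold-change and a ratio of fold-changes arise only from a difference of logs, so an experienced programmer would take the rule as shorthand for log baseline as covariate and change on the log scale as response. That stands, and it makes the first part an error of wording and not an unworkable analysis.

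It is also fair that the plan is silent on the Month 9 scale and does not prescribe ng/L; that the output sentence may be meant for both models; and that the NT-proBNP MMRM has Month 9 as a visit, with estimates at both visits to be presented under Section 4.4.1.2. A log-scale Month 9 estimate is therefore already planned. This does not remove the gap: the same visit would carry two estimates, and the plan does not say whether they share a scale.

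Three stronger readings are tempting and are not supported.

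- That the MMRM will discard improving patients, and more of them in one arm. This needs the literal rule to be programmed against the output promised in the next sentence, and any percentage would rest on an assumed fold-change and spread that the SAP does not give.
- That Month 9 is specified in raw ng/L. No scale is specified.
- That the Month 9 result would be driven by a few very high values because up to 15% of patients may exceed 3000 ng/L at baseline. Section 1.4 only caps enrolment above a threshold; it says nothing about how extreme those values are.

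**Conclusion.** The point holds as a specification error in current text. As written, the MMRM response is undefined for any patient whose NT-proBNP falls or is unchanged, and it is inconsistent with the output promised for it. The scale of the Month 9 imputation and ANCOVA is not stated. The first conclusion is algebra and rests on no assumption about the data; the second rests on reading Sections 4.4.4 and 4.4.1.1 together.

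The consequence is minor. Section 1.2 lists NT-proBNP as exploratory, it appears in neither multiple comparisons procedure (Sections 1.3.1 and 1.3.2), and Section 4.4 treats p-values outside the formal testing as descriptive. Primary and secondary conclusions are untouched. No numerical bias can be put on it from this document.

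**What to change.** In Section 4.4.4, replace the transformation sentence with:

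> The response is log(postbaseline NT-proBNP) minus log(baseline NT-proBNP), with log baseline as covariate, for both the Month 9 ANCOVA/MI (imputing on the log scale) and the Month 18 MMRM; LS means and differences are exponentiated to give geometric mean fold-changes and their ratio.

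The cost is one sentence. It needs no new data and no change to the model terms, populations or promised output, and it puts both Month 9 estimates on one scale.
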